4.1. Randomization

A random number generator program will be used to assign sequential qualified study cases to control group (N = 69) or SuperNO₂VA™EtCO₂ group (N = 69) before collection of additional demographic information and before anesthetic and surgical care. After study group assignment, baseline data will be collected, including age, gender, height, weight, and BMI.

4.2. Planned Statistical Analysis

Although randomization into treatment groups should minimize differences between the groups, basic bivariate analyses will be performed to determine if there are any clinical or demographic differences, using the data collected in table 1. Logistic regression models will be performed to determine if there are significant differences between the groups for both incidence and severity. Student's t-tests will be performed to determine if there is a significant difference between groups for duration, with Wilcoxon non-parametric tests being performed if the data are non-linear. If significant differences in clinical or demographics characteristics were found, multivariable models will be performed to adjust for these possible confounding variables using logistic regression and ANCOVA models (with GEE models being used to model non-linear data with the appropriate exponential family distribution). All analytic assumptions will be verified and all analyses performed with SAS v9.4, SAS Institute, Cary, NC), analyzing the data as both per-protocol and intention-to-treat.

A Data Safety and Monitoring Board (DSMB) will be convened once half the necessary study population has been enrolled, to discuss the current status of primary endpoints and adverse events, all of which will be tabulated throughout the study. If effect sizes are larger than originally planned and there is a statistically significant decrease in the primary event at this halfway mark, the study will end at this time.

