Effect of nasal positive airway pressure versus standard care on oxygenation and ventilation during propofol- based sedation for colonoscopy in patients with high risk of airway obstruction: a prospective randomized controlled trial.

NCT05524220

Version Date: 01/27/2023

Effect of nasal positive airway pressure versus standard care on oxygenation and ventilation during propofol-based sedation for colonoscopy in patients with high risk of airway obstruction: a prospective randomized controlled trial.

Principal Investigator: [name]

Co-PIs: [name]

[name]

[name]

[name].

Statistician: [name], M.S.

Contacts:

[name]., VP, Medical Director
Vyaire Medical
[REDACTED]
[REDACTED]

SUMMARY TABLE

Title	Effect of nasal positive airway pressure versus standard care on oxygenation and ventilation during propofol-based sedation for colonoscopy in male and female patients with high risk of airway obstruction: a prospective randomized controlled trial.
Project Office	
Study Size (# of patients)	150 patients
Study Design	Prospective randomized controlled single site trial.
Primary Outcome	Elapsed time from initiation of induction to the first airway intervention.

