1. OBJECTIVES

Primary Objective

The primary objective of the study is to prospectively and randomly compare elapsed time from initiation of induction to the first airway intervention in patients considered high risk for hypoxia (ie: BMI ≥ 35 kg/m² and/or documented Obstructive Sleep Apnea).

Endpoints of Interest

1. Compare the amount of propofol administered during induction and total dose administered for procedure
2. Compare Modified Observer's Assessment of Alertness/Sedation Scale (MOAAS) scores immediately prior to endoscopic intubation and during the procedure
3. Compare the length of time from induction to endoscopic insertion
4. Compare the incidence and duration of procedural interruptions (ie: number of times and length of time the endoscope is removed from the patient)
5. Compare the incidence, duration, and reason for airway maneuvers
6. Compare the length of time for the procedure (ie: length of time from procedure start to procedure end)
7. Compare recovery times
8. Compare patient satisfaction scores (visual analog scale (VAS)) immediately after procedure
9. Compare patient tolerance to SuperNO₂VA EtCO₂ compared to control (ie: face mask at 10LPM)
10. Compare endoscopist satisfaction scores for
11. Compare anesthesiologists satisfaction scores
12. Compare the incidence of cardiac complications

Study Design

This is a prospective randomized controlled single site trial.

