90 seconds until the MOAA/S is <4. The measurements that will be made are the following: Elapsed time from initiation of induction to the first disappearance of expired CO₂ on capnography, the incidence, severity, and time of oxygen desaturation, number of airway maneuvers performed, duration of airway maneuvers, reason for performing the airway maneuver, the onset time of administration of sedation, the duration of the procedure, the total dosage of the medication, vital signs - blood pressure, heart rate, and oxygen saturation, the time to full recovery, and patient cooperation. Nursing or the research assistant will document their patient's depth of sedation, cooperation with procedure, and safety. Patients will recover in the endoscopy suite. The patients will have continuous monitoring of heart rate, O₂ saturation, and BP monitoring and MOAAS Score. The time to discharge will be obtained for each patient. Patients will also complete a satisfaction and pain questionnaire before they are discharged. A statistician using student T-test, Fishers exact test, and other statistical methods they deem appropriate will analyze the collected data.

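### The primary outcome is a time to first airway intervention, but the analysis plan has no rule for a patient who never needs one

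*Combined protocol and SAP*

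**What the plan says.** The Summary Table gives the primary outcome as "Elapsed time from initiation of induction to the first airway intervention", and Section 1 repeats it as the primary objective.

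Section 4.2 (Planned Statistical Analysis) does not mention this outcome by name. For times it says that "t-tests will be performed to determine if there is a significant difference between groups for duration", with a Wilcoxon test if the data are not linear. ANCOVA and GEE models appear only as adjusted analyses, to be run if baseline differences are found. For binary outcomes it says "Logistic regression models will be performed to determine if there are significant differences between the groups for both incidence and severity". It promises "analyzing the data as both per-protocol and intention-to-treat". Section 5.2 (Methods) adds that the t-test, Fisher's exact test and "other statistical methods they deem appropriate will analyze the collected data".

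Two places suggest that some patients will have no event. Item 5 of the endpoints in Section 1 is "Compare the incidence, duration, and reason for airway maneuvers". The stopping sentence in Section 4.2 refers to a significant decrease in the primary event. Neither place gives an expected share.

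No section mentions censoring, a survival method, or a substitute value or rank for a patient without an intervention.

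**The concern.** A time to a first event is not observed in a patient who never has the event. A t-test needs a number for everyone it includes, and a Wilcoxon test needs a rank. Without a rule, the analyst has two obvious shortcuts.

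- **Drop event-free patients.** The comparison is then made in a subset selected by a post-randomisation outcome, which conflicts with the promised intention-to-treat analysis.
- **Enter the end of the procedure as their time.** Procedure length, itself a secondary endpoint (Section 1, item 6), then becomes part of the primary result.

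The open clause in Section 5.2 lets the rule be chosen after data are seen. An interim efficacy look is also planned, and Section 4.2 ends the trial there if the primary result is significant and the effect is larger than planned. The choice of rule could therefore decide early stopping.

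**Working it through.** **1. The plan's own figure.** Section 10.1 uses n = 2(Z_α + Z_{1-β})²σ²/Δ² with Δ = 5, σ = 10, α = 0.05 (taken as two-sided) and power 0.80.

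- n = 2 × (1.96 + 0.8416)² × 100/25 = 62.8 per arm, and 62.8 × 1.20 = 75.3. The stated 75 per arm is reproduced.
- That t-test has 86% power at 75 per arm and 78% at 60 (75 less 20%).
- The formula assumes that every analysed patient has an observed time. The Brief Analysis Plan quotes 19 ± 10 versus 10 ± 12 minutes from the source study. The documents do not say whether those means include patients without an intervention.

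**2. Assumptions for the illustration.** The documents give no procedure length, event-free share or time distribution. Assumed here: procedure end Normal with SD 6 minutes and mean 25, 28 or 30 (floored at 5); 60 or 75 per arm; two-sided 5% tests; 10,000 simulated trials per cell.

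**3. Error rate with no airway effect.** Times are exponential with the same mean m in both arms, and procedures average 25 versus 30 minutes. Ignoring the floor, the event-free share in an arm with mean procedure length μ is exp(−μ/m + 36/(2m²)). The mean of the shorter of event time and procedure end is m × (1 − share). The spurious mean difference in the procedure-end t-test is therefore m × (difference in shares).

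| m | Event-free share | Spurious difference | Procedure-end t | Events-only t | Log-rank |
|---|---|---|---|---|---|
| 10 | 9.8% vs 6.0% | 0.4 min | about 5% | 7-8% | 5-6% |
| 20 | 30.0% vs 23.3% | 1.3 min | 10-12% | 10-13% | 5-6% |
| 40 | 54.1% vs 47.8% | 2.5 min | 28-34% | 12-14% | 5-6% |

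A Wilcoxon test with event-free patients tied and ranked last rejects in 5-7%. With a 3-minute gap instead of 5, the procedure-end figure in the last row falls to about 14-17%. With equal procedure lengths, every method is at about 5% in every row.

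**4. Power, 60 per arm, equal procedure lengths in both arms.**

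| Scenario | Events-only t | Procedure-end t | Rank-last Wilcoxon | Log-rank |
|---|---|---|---|---|
| Exponential, 10 vs 19 min | 36-46% | 85-87% | 83% | 89-90% |
| Exponential, 10 vs 15 min | 21-26% | 48-53% | 45-47% | 52-56% |
| Weibull, 10 vs 15 min, SD 10 both arms | 86-89% | 87-89% | 93% | 76-80% |

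The exponential rows do not match the planning SD of 10 at a mean of 15 or 19, because an exponential SD equals its mean. The events-only figures also depend on the equal lengths: at 25 versus 30 minutes the first one becomes about 65%.

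**5. The estimate moves too.** In a separate simulation (60 per arm, assumed hazard ratio 0.5, assumed median sedation 25 minutes), 70% of controls and 46% of device patients had an event. The estimated difference was 1.8 minutes with event patients only and 4.5 minutes with end of sedation entered as the time.

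**The case against.** Several points on the other side stand.

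- **The logistic regression sentence does not show that event-free patients are planned for.** A reader might infer this. However, the one outcome that the protocol describes by both incidence and severity is oxygen desaturation (Section 5.2); maneuvers are never given a severity. The support comes from endpoint item 5 and the stopping sentence. They make event-free patients foreseeable, not certain.
- **Section 4.2 never ties its duration tests to the primary outcome.** The link is the natural reading, but it is an inference. If it is wrong, the primary outcome has no named test at all.
- **The largest error figures need two unsupported conditions together:** about half the patients event-free, and a 5-minute difference in procedure length. Nothing in the documents suggests such a difference.
- **The shortcuts do not always cost power.** At 10 versus 15 minutes with SD 10, both keep 86-89%, above the log-rank test.
- **Last scope removal is not a clean censoring time.** The maneuver definition in Section 5.3 is not limited to the time the scope is in place, and a scope may be removed because of a respiratory complication.

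The planned Wilcoxon test does not answer the concern. It depends on a vague condition and still needs a rank for event-free patients. Leaving the choice to the statistician is the gap itself.

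**Conclusion.** The omission is certain: the primary outcome can be missing by design, and no rule covers that case. It should be settled before any outcome data are seen.

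The impact is not certain. It is nil if every patient needs an intervention, small if fewer than about 10% do not, and material if about half do not and procedure lengths differ. All error and power figures rest on the assumptions listed above and show direction and scale only.

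A reader might infer that the primary test cannot be run on all randomised patients, that the trial's error rate is about 30%, or that dropping event-free patients always loses power. The documents support none of these. The first is true only if event-free patients occur, the second needs both conditions named above, and the power loss ranges from large to none.

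**What to change.** Add to Section 4.2:

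> The primary analysis includes all randomised patients by assigned group. The event is the first airway maneuver (Section 5.3), timed from the start of induction. Patients with no maneuver are censored at the end of the recorded observation period for maneuvers, a single time point fixed in advance and identical in definition for both groups. Patients withdrawn earlier are censored at withdrawal. Groups are compared by a two-sided log-rank test with Kaplan-Meier curves. The same test is used at the interim look, and time after crossover counts in the assigned group. A Wilcoxon test ranking event-free patients last is a sensitivity analysis.

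Keep the t-test/Wilcoxon rule for durations that every patient has.

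Make sure that the clock times of the first maneuver and of the end of observation are recorded. The only elapsed time to a first event in the Section 5.2 measurement list is "Elapsed time from initiation of induction to the first disappearance of expired" CO₂. The data form is not among the documents, so it may already hold these times.

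In Section 10.1, state that 75 per arm was derived for a fully observed mean difference, and restate power for the log-rank test under stated assumptions. For 10 versus 15 minutes with equal procedure lengths and 60 to 75 per arm, it is 52-65% if times are exponential and 76-88% with SD 10 in both arms.

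**Cost:** one paragraph, a few lines of SAS and two recorded times, with no added patients or visits. The headline is no longer a mean difference in minutes. The log-rank test is also weaker than the rank-last Wilcoxon if the device mainly delays early events (about 76-80% versus 93% at 10 versus 15 minutes, SD 10, equal procedure lengths, 60 per arm).

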Secondary Outcome	
 1. Compare the amount of propofol administered during induction and total dose administered for procedure 2. Compare Modified Observer's Assessment of Alertness/Sedation Scale (MOAAS) scores immediately prior to endoscopic intubation and during the procedure 3. Compare the length of time from induction to endoscopic insertion 4. Compare the incidence and duration of procedural interruptions (ie: number of times and length of time the endoscope is removed from the patient) 5. Compare the incidence, duration, and reason for airway maneuvers 6. Compare the length of time for the procedure (ie: length of time from procedure start to procedure end) 7. Compare recovery times 
 a. Ready to discharge b. Actual discharge 8. Compare patient satisfaction scores (visual analog scale (VAS)) immediately after procedure 
 a. Overall experience b. Quality of sedation c. Pain experienced during procedure d. Pain after the procedure e. Nausea after awakening f. Vomiting after awakening g. Dizziness after awakening h. Recollection of scope insertion i. Recollection of scope removal j. Awake during the procedure 9. Compare patient tolerance to SuperNO₂VA™EtCO₂ compared to control (ie: face mask at 10LPM) 10. Compare anesthesiologists satisfaction scores 
 a. Overall experience b. Rating of sedation c. Difficulty of patient to sedate 11. Compare the incidence of cardiac complications
Inclusion Criteria	
 1. Age 18 years of age or older 2. All Patients undergoing colonoscopy (male and Female) 3. American Society of Anesthesiology (ASA) Physical Status I-III 4. BMI $\geq 30 \text{ kg/m}^2$ or documented Obstructive Sleep Apnea

	5. Has provided written informed consent

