5.3 Definitions of Events

- Airway maneuver: consists of either airway maneuvers such as chin lift, jaw thrust, , mask ventilation, or the insertion of a nasal or oral airway, supraglottic device, or ETT
- Oxygen desaturation: SpO₂ ≤ 90% for ≥ 15 seconds
- Cardiac complications is defined by a change in either SBP or DBP > 25% from baseline, a change in heart rate > 25% from baseline, arrhythmias, and ST-changes on EKG (ST depression or elevation).
- Full recovery is defined as the time from endoscope withdrawal until a MOAA/S score of 5 was achieved and the patient could drink liquids and ambulate independently.
- Full recovery until actual discharge is defined as the interval from full recovery until the patient exited the recovery room.
- Induction to full sedation is the time from initial administration of intravenous sedative or analgesic to the insertion of the endoscope
- Intra-procedural period was defined as the time of first scope insertion until the last scope removal.
- Procedural interruption is defined as the removal of the endoscope due to a respiratory complication
- Modified Observer's Assessment of Alertness/Sedation Scale (MOAAS) from 1 – 5

MOAAS:

- 0 No response after painful trapezius squeeze
- 1 Responds only after painful trapezius squeeze
- 2 Responds only after mild prodding or shaking
- 3 Responds only after name is called loudly and/or repeatedly
- 4 Lethargic response to name spoken in normal tone
- 5 Responds to name spoken in normal tone

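### For airway maneuvers and interruptions, the plan does not say how event-free patients enter the duration test; an events-only comparison can miss a benefit or show it as longer durations

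*Combined protocol and SAP*

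**What the plan says.** The Summary Table and Section 1 list two secondary comparisons that have a duration part: "Compare the incidence and duration of procedural interruptions" (outcome 4) and "Compare the incidence, duration, and reason for airway maneuvers" (outcome 5).

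Both depend on an event after randomisation. Section 5.3 states: "Procedural interruption is defined as the removal of the endoscope due to a respiratory complication". The same section defines an airway maneuver as an act performed on the patient, from a chin lift up to and including "or the insertion of a nasal or oral airway, supraglottic device, or ETT".

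Section 4.2 handles the two parts separately. For incidence: "Logistic regression models will be performed to determine if there are significant differences between the groups for both incidence and severity". The rule for duration is a two-group comparison: "t-tests will be performed to determine if there is a significant difference between groups for duration". The section then adds a fallback: "with Wilcoxon non-parametric tests being performed if the data are non-linear". It asks for both per-protocol and intention-to-treat analyses, and for adjustment for baseline characteristics that differ significantly. Section 5.2 lists among the measurements "number of airway maneuvers performed, duration of airway maneuvers, reason for performing the airway maneuver".

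Nowhere does the document say whether a patient without a maneuver or interruption counts as zero or is left out, or how several episodes in one patient are combined.

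**The concern.** Incidence has its own test and event-free patients are given no duration, so the natural reading of the duration test is a comparison among patients who had an event. Whether a patient has an event is an outcome that the device is meant to change. The two subsets are therefore no longer comparable by randomisation. If the device mainly prevents brief episodes, the ones left in its arm are the longer ones, and their mean rises although no episode was lengthened.

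The other provisions of Section 4.2 do not cure this. A Wilcoxon test on the same subset carries the same selection. The adjustment covers baseline characteristics only. An intention-to-treat label cannot bring back patients who have no value. At stake is the duration part of two secondary outcomes that bear directly on airway support.

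**Working it through.** **The plan's own figure.** No figure is given for these durations. The only planning number used here is the 75 per arm of Section 10.1: 2 × (1.960 + 0.842)² × 10² / 5² = 62.79, and 62.79 × 1.2 = 75.35. The stated 75 reproduces.

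**Assumed inputs.** The documents give no event rates or duration distributions. Assumed: 70% of controls have an event, one duration per patient, lognormal with median 60 s and log-SD 0.8, two-sided 5% tests. The device only prevents episodes and never lengthens one.

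**Expected values (Φ is the normal distribution function).**
- Control mean among patients with an event: 60 × exp(0.8²/2) = 82.63 s. Per randomised patient: 0.70 × 82.63 = 57.8 s.
- Shortest half abolished: device mean 82.63 × Φ(0.8)/0.5 = 82.63 × 0.7881/0.5 = 130.24 s. Per randomised patient: 0.70 × 0.50 × 130.24 = 45.6 s.
- Shortest quarter abolished: 82.63 × Φ(0.8 + 0.674)/0.75 = 82.63 × 0.9298/0.75 = 102.4 s. Per randomised patient: 0.70 × 0.75 × 102.4 = 53.8 s.
- 65% of below-median and 35% of above-median episodes prevented: the short half has mean (82.63 − 0.5 × 130.24)/0.5 = 35.0 s, so the device mean is (0.175 × 35.0 + 0.325 × 130.24)/0.50 = 96.9 s. Per randomised patient: 0.70 × 0.50 × 96.9 = 33.9 s.
- Half of all episodes prevented regardless of length: the device mean stays at 82.63 s. Per randomised patient: 0.70 × 0.50 × 82.63 = 28.9 s.

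Time per randomised patient falls in every case. The mean among patients with an event stays level or rises.

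**Simulated trials, 75 per arm.**

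| What the device prevents | Mean with an event, control vs device (s) | Total per randomised patient, control vs device (s) | Events-only t-test: longer on device |
|---|---|---|---|
| Half, regardless of length | 82.6 vs 82.6 | 57.8 vs 28.9 | about 3% |
| 65% of short, 35% of long | 82.6 vs 96.9 | 57.8 vs 33.9 | about 12% |
| Shortest quarter | 82.6 vs 102.4 | 57.8 vs 53.8 | about 23% |
| Shortest half | 82.6 vs 130.2 | 57.8 vs 45.6 | about 72% |

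The events-only Wilcoxon does not help: it reports longer durations in about 17%, 53% and 98% in the last three rows. A Wilcoxon on all randomised patients, with 0 for no event, almost never reports longer. It finds the benefit in 95–98% of trials in the first two rows and in about 70% in the last. In the shortest-quarter row the true fall is only 4 s per patient, so there is little to detect.

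**A second duration model.** Assume 70% of events are brief (mean 1 min) and 30% long (mean 4 min), log-SD 0.5, a control event rate of 50%, and a device that prevents 80% of brief and 20% of long events. The control mean with an event is 0.7 × 1 + 0.3 × 4 = 1.90 min. The device mean is (0.14 × 1 + 0.24 × 4)/0.38 = 2.89 min. Per randomised patient the values are 0.50 × 1.90 = 0.95 and 0.50 × 0.38 × 2.89 = 0.55 min. The events-only t-test reports longer in 38% of trials and the zero-filled Wilcoxon finds shorter in 95%. Over event rates of 30–70% and four patterns that favour brief events, the events-only t-test reports longer in 12–59%. With equal prevention it reports longer in about 3% and shorter in only 1–2%, so a halving of events goes unseen. With zeros, longer is reported in at most 0.2% of trials in any scenario.

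**The case against.** Section 4.2 never restricts the duration test to patients with an event. An intention-to-treat comparison with zeros would also fit its words, and then the reversal disappears. A reader might infer that the plan prescribes an events-only test. It does not: it is silent, and the firm defect is the missing rule. The silence still matters, because it leaves a choice after the data are seen between two analyses that can point in opposite directions.

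The large reversal rates also need strong assumptions. If the shortest half is abolished and the remaining episodes are shortened by 40%, the events-only t-test reports longer in only 1% of trials and the Wilcoxon in 8%. Nothing in the documents says that the device spares long episodes. This stands: reversal is possible, not expected.

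Nor is the randomised comparison lost for outcomes 4 and 5 as a whole, as one might conclude. Incidence is tested separately. In the shortest-half scenario an exact test of incidence on all randomised patients detects the benefit in 99% of trials, and a reader would see it beside the duration result.

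Interruptions may be too rare for much harm. At an assumed event rate of 5–10%, even with the shortest half abolished, the t-test reports longer in roughly 7–18% of trials, with about 2–4 device-arm events.

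Two further inferences are not supported. The plan does not say that repeated episodes will be treated as independent, and the simulations have at most one episode per patient. That a few inserted airways would dominate the mean cannot be shown either, since Section 5.3 does not say how an inserted airway is timed.

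**Conclusion.** The point holds for the duration part of secondary outcomes 4 and 5 only. The plan compares a quantity that event-free patients do not have, and states neither a value for them nor a rule for combining episodes. On the natural reading, the comparison can miss a real reduction in airway-support time. It can also report longer durations on the device if brief episodes are prevented preferentially: from about 3% of trials with no preference to about 72% at the extreme of full truncation. These rates rest on assumed event rates and durations, with Monte Carlo error of about one percentage point. The incidence tests, the primary outcome, procedure time and recovery times are unaffected. The change is worth making before analysis, as an improvement to secondary outcomes.

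**What to change.** In Section 4.2, for outcomes 4 and 5, define duration as total time per randomised patient: the sum over that patient's episodes, 0 if none. Compare all patients in the arm assigned by a Wilcoxon test, and give the mean difference with a bootstrap 95% confidence interval. Report durations among patients with an event descriptively only, beside incidence. Report inserted airways separately from manual maneuvers only if maneuver type is recorded; the measurement list in Section 5.2 does not name it.

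The cost is mainly wording. Section 5.2 already lists number and duration of maneuvers. It does not list the length of interruptions, although outcome 4 calls for it, so the case report form should be checked. The downside is statistical: totals with many zeros are skewed, so the mean difference will have a wide interval, and interruptions may be too rare for a useful test.

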Exclusion criteria	
 1. Inpatient status 2. Active Congestive Heart Failure Exacerbation 3. Untreated ischemic heart disease 4. Acute exacerbation of respiratory disorders, including COPD and asthma 5. Emergent procedures 6. Pregnancy 7. Previous enrollment in this study 8. Inability to provide informed consent 9. Additional medical testing planned for the same day 10. History of allergic reaction to Propofol 11. Tracheostomy 12. Supra-glottic or sub-glottic tumor 13. Gastrointestinal tract obstruction or delayed transit (including delayed gastric emptying, gastric bezoar, achalasia, toxic megacolon). 14. Prisoners 15. Unable to fit SuperNoVa
Study Procedures	
Pretreatment Evaluation	Candidates will be assessed if the SuperNova fit is difficult or impossible
On-Study Visits	N/A
Follow-up Visits	N/A
End of Study Visit	Subjects will be assessed in PACU before he or she is discharged
Brief Analysis Plan	
Based on the literature, the elapsed time from anesthesia induction to the first airway intervention was 19 ± 10 min in the Mask group ($n=63$) vs. 10 ± 12 min in the Control group ($n=73$, $P < 0.001$)¹⁵. For sample size calculation we used the standard sample size calculation equation¹⁶:
 $n = \frac{2(Z_{\alpha} + Z_{1-\beta})^2 \sigma^2}{\Delta^2}$ 
σ = variation of the measurement Δ = difference to be detected
 
σ and Δ are based on the outcome values from previous publication.¹⁵ This publication showed a time difference (Δ) of 9 minutes with a standard deviation (σ) of ± 10 minutes in both intervention groups. To be able to detect an even smaller time difference of 5 minutes and with a standard deviation of 10 minutes and a drop of percentage of 20% ($\alpha = 0,05$ and $1-\beta = 0,80$) we calculated $n_1=n_2= 75$. A total of 150 patients will be enrolled.

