5.4 Crossover to Other Group After Randomization

Patients in either Group A or Group B will be eligible for crossover to the other group at the discretion of the anesthesiologist in order to safely complete the procedure and minimize the likelihood of future adverse events.

Group A (Standard care with a facemask) to Group B (SuperNO₂VA™EtCO₂) group will occur when during the procedure either: 1) after insertion of an oral or nasal airway and hypoxia is persistent, and 2) before supraglottic airway endo tracheal tube insertion if the care team wishes.

Group B to Group A: If any of the following occur: 1) patient refusal to wear the mask once placed due to claustrophobia, poor fit or discomfort or any other reason; 2) if a nasal or oral airway is needed.

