10. SAMPLE SIZE DETERMINATION AND DATA ANALYSIS

10.1 Sample Size Determination

For sample size calculation we used the standard sample size calculation equation¹⁶:

$$n = \frac{2(Z_{\alpha} + Z_{1-\beta})^2\sigma^2}{\Delta^2}$$

σ = variation of the measurement

Δ = difference to be detected

σ and Δ are based on the outcome values from previous publication.¹⁵

This publication showed a time difference (Δ) of 9 minutes with a standard deviation (σ) of ± 10 minutes in both intervention groups.

To be able to detect an even smaller time difference of 5 minutes and with a standard deviation of 10 minutes and a drop of percentage of 20% ($\alpha = 0,05$ and $1-\beta = 0,80$) we calculated $n_1=n_2= 75$. A total of 150 patients will be enrolled.

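### Baseline significance tests decide which covariates are adjusted for, so BMI and documented OSA usually go unadjusted, and no primary analysis of the primary outcome is named

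*Combined protocol and SAP*

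**What the plan says.** Section 4.2 (Planned Statistical Analysis) starts from the Table 1 data: "basic bivariate analyses will be performed to determine if there are any clinical or demographic differences, using the data collected in table 1". Adjustment depends on the result: "If significant differences in clinical or demographics characteristics were found, multivariable models will be performed to adjust for these possible confounding variables". The adjusted models are logistic regression and ANCOVA, with GEE as a further option.

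For time outcomes, "t-tests will be performed to determine if there is a significant difference between groups for duration". The stated fallback is a rank test, "with Wilcoxon non-parametric tests being performed if the data are non-linear". I take the primary outcome, elapsed time from induction to first airway intervention, to be one of these durations. Everything is done twice, "analyzing the data as both per-protocol and intention-to-treat". Section 5.2 (Methods) also leaves further methods to the statistician's judgement.

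No covariate is named anywhere. Section 5.2 describes randomisation in groups of ten and section 4.1 (Randomization) a random number generator; neither mentions stratification. Yet BMI and documented OSA define eligibility (section 2.2), are described as risk factors for hypoxemia (Background and section 2.3), and are already collected in Table 1.

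**The concern.** Adjustment in a randomised trial is worth having when the covariate predicts the outcome. A baseline p-value does not measure that. In the as-randomised comparison it reflects only the play of chance in allocation. In the per-protocol set it can also reflect who crossed over or withdrew: section 5.4 says patients "will be eligible for crossover to the other group at the discretion of the anesthesiologist", and section 6 allows withdrawal. The covariates are therefore picked by a criterion unrelated to their purpose, and the two analysis sets can end up with different adjusted models.

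Two things are at stake. The variables most likely to matter, on the protocol's own account, will usually be left out. And when a model is triggered, the trial will have an unadjusted and an adjusted result for the same outcome, with nothing in the plan to say which one counts.

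**Working it through.** **The plan's own figure.** Section 10.1 uses a 5-minute difference, SD 10, alpha 0.05 and power 0.80, "with a standard deviation of 10 minutes and a drop of percentage of 20" per cent. Two-sided, n = 2(1.960 + 0.842)² × 10² / 5² = 62.79 per arm, and 62.79 × 1.2 = 75.35, which matches the stated 75. Removing 20% from 75 leaves 60 analysed per arm, used below.

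**How often a model is triggered.** Table 1 has 10 rows. Counting its 11 co-morbidities singly gives 9 + 11 = 20 variables. The plan states no level for the baseline tests; I assume 0.05 and independence.
- 10 tests: 1 − 0.95¹⁰ = 0.401.
- 20 tests: 1 − 0.95²⁰ = 0.642.

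Height, weight, BMI, OSA and STOP-BANG are linked. A simulation allowing for this gave 36–37% and 61–62%, so the independent figures are slightly high.

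**How often BMI and OSA go unadjusted, all trials.**
- BMI and both OSA rows: 0.95³ = 0.857.
- BMI and one OSA variable: 0.95² = 0.903.

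This gives 86–90%, which includes trials where no adjusted model is fitted.

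**The same, given that a model is fitted.** The formula is (0.95ᵏ − 0.95ᵐ) / (1 − 0.95ᵐ), with m tests in all and k of them for BMI and OSA.
- m = 10: (0.857 − 0.599)/0.401 = 0.64 for k = 3; (0.903 − 0.599)/0.401 = 0.76 for k = 2.
- m = 20: (0.857 − 0.358)/0.642 = 0.78 for k = 3; (0.903 − 0.358)/0.642 = 0.85 for k = 2.

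**Power.** Unadjusted: noncentrality 5/(10√(2/60)) = 2.739 on 118 df, power 77.5% (78.2% by the normal approximation). With BMI (1 df) and three-level OSA (2 df), residual df are 120 − 2 − 3 = 115. The residual variance is multiplied by (1 − R²), and chance imbalance multiplies the variance of the treatment difference by about 1 + 3/114.

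| Assumed R² | Power | Change, points |
|---|---|---|
| 1% | 76.9% | −0.7 |
| 5% | 78.5% | +1.0 |
| 10% | 80.7% | +3.1 |
| 20% | 85.0% | +7.5 |

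In simulations where the triggered model replaced the t-test, power was about 76–79%, so the plan's rule captures little of any gain.

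**Type I error.** In simulations with 60 per arm (10,000 trials, Monte Carlo standard error 0.002), each single rule stayed near nominal: unadjusted 4.4–5.0%, triggered 4.1–5.0%, always adjusted 4.4–5.3%. Taking the better of the unadjusted and triggered results gave 4.9–5.4% (10 variables) or 5.7–5.9% (20).

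**The case against.** The strongest reply is that the harm is small and partly assumed. This stands. The documents link BMI and OSA to hypoxemia, not to time to first airway intervention, so R-squared is unknown. Eligibility on BMI or OSA may also narrow the spread of these covariates and hence what they explain. At 1% there is a slight loss, and only at the assumed 20% does the gain exceed seven points.

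A second reply is that the unadjusted comparison is the natural primary: section 10.1 sizes the trial on two unadjusted means, and section 5.2 names the t-test. That is a fair inference, but the plan never states it, and section 4.2 gives no rule for a triggered model that disagrees. The primary outcome is named; its primary analysis is not.

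A reader might also infer more than the documents support:
- That baseline testing inflates type I error. It does not under any one fixed rule. A figure near 6% needs both 20 variables and someone choosing the better result.
- That the 86–90% describes fitted adjusted models. It covers all trials; among fitted models the range is 64–85%.
- That the covariate set is the only data-dependent element. Whether any adjusted model is fitted, and whether Wilcoxon or GEE is used, also depend on the data. The Wilcoxon clause can even be read as replacing the t-test.
- That the 20% drop separates intention-to-treat from per-protocol. Section 10.1 does not say so; crossover and withdrawal are the supported reasons.
- That the trigger will be applied at the interim. The documents do not state this.

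**Conclusion.** The concern holds in a limited form. Covariates are chosen by significance tests that carry no information on prognosis, the two risk factors the protocol names usually go unadjusted, and no primary analysis is named for the primary outcome. The cost is mainly precision: from about one point of power lost to about seven gained by fixing BMI and OSA, for an R-squared of 1% to 20%. That range rests on assumption, as do the 0.05 level and the independence of the baseline tests. The existence of the rule and the missing designation rest on the text alone. This is a cheap improvement that should be made; it is not a threat to the trial's validity.

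**What to change.** In section 4.2:
- Delete the significance trigger and report Table 1 descriptively by arm.
- For the primary outcome, prespecify BMI (continuous) and documented OSA status (on home CPAP, not on home CPAP, none documented) as fixed covariates. State that the last level includes undiagnosed OSA.
- Name that adjusted comparison as the primary analysis, with the unadjusted comparison supportive.
- Use the same covariates in the intention-to-treat and per-protocol analyses and in any interim efficacy analysis.

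The choice between t-test, Wilcoxon and GEE, and the handling of patients with no airway intervention, are separate matters. The same covariates carry over if the primary model changes, for example to time-to-event.

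The cost is plan wording and three degrees of freedom. ANCOVA is already named and both covariates are already collected. The downside is about one point of power if the covariates explain 1% of the variance or less. Sample size does not change. The wording should be settled before outcome data are examined by arm.
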